ANNEX II.- RESCUE ANALGESIC TREATMENT:

- Review patient treatment in URPA and in the hospitalization floor. Do not administer scheduled analgesia unless the patient demands it, and for the same reason always leave a scheduled rescue . If necessary, notify the Resident of the Anesthesiology Guard (Virgen de la Vega Hospital building). Evaluate your pain and write down the elapsed time.
- **Paracetamol** 1 gr/ 6 h iv. If contraindication or allergy: Metamizol 2g/8 h iv. _
- If you need more analgesia and the 6 h has not passed:
- **Dexketoprofen** 50 mg iv/ 8 h.
- If contraindication to NSAIDs or pain persists:
- **Ondansetron** bolus 4mg iv and **Tramadol** infusion 200 mg iv + **Metamizol** 6 gr diluted in 500 cc S. Physiological to pass in 24 h (20ml/h). And discontinue Paracetamol, except in those allergic to Metamizole.
- Follow-up of the patient 48 h.

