2. INTRODUCTION

The increase in life expectancy together with very low birth rates is causing an accelerated growth in the percentage of older people, which results in an increase in the aging of the population, especially in the industrialized world. In our country, the phenomenon of aging is even more accelerated, since in less than 30 years the number of people over 65 years of age has doubled. Current data in Spain show that the population over 65 years of age is around 17% of the total population, with more than 7 million people (National Institute of Statistics-INE, 2008), of which approximately 25% are octogenarians. As a consequence, it is increasingly common to find in clinical practice elderly patients who require treatment of diseases and complications that are typical of advanced age.

Among these is the hip fracture, which presents a serious problem of morbidity and mortality for patients, and has a great impact on health costs due to both its treatment and the complications derived. It is estimated that there are 1.6 million fractures per year worldwide, with more than 610,000 fractures per year in Europe, and in Spain 45,000 fractures occur annually in older people(1, 2) of 65 years, being 80% over 75 years of age and with an associated annual mortality of about 30%(3, 4). Hip fracture is one of the most frequent surgical diagnoses in our environment. A very old and multipathological population, generally polymedicated and in which the presence of neurodegenerative diseases is not uncommon, makes it a very fragile population, which can sometimes have difficulty expressing its feelings, including pain, which is usually underdiagnosed(5). We must offer these patients an effective analgesic treatment from the first moment, avoiding the use of opioids and any drug that may deteriorate their cognitive faculties, and minimizing the use of usual analgesics (some of them, such as NSAIDs, can affect the control of blood pressure and already decreased renal function). Pain control in these patients is very important because it facilitates post-surgery recovery and early mobilization, and reduces the time of hospitalization after surgery, and the appearance of complications such as delirium, infections or thromboembolism(6). In addition, it accelerates the initiation of rehabilitation and functional recovery of elderly patients.

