3. HYPOTHESES AND OBJECTIVES

3.1. HYPOTHESIS:

Levobupivacaine has advantages over Ropivacaine in the combined blockade (PENG - pericapsular nerve group- and the femoral lateral cutaneous nerve -BNFCL-) in hip fractures of the elderly, since a better analgesic control, similar latency period, and a longer analgesic duration are obtained.

3.2. OBJECTIVES:

3.2.1. MAIN:

- To compare the analgesic efficacy of both local anaesthetics in the regional blockade of hip fracture surgery.

3.2.2. SECONDARY:

- To describe the behavior of this combined technique in hip fractures, establishing latency of onset and duration of analgesia.
- Describe the side effects derived from the described combined technique. To validate in our population, especially in patients with cognitive impairment, the usefulness of the analgesic scales chosen.

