6.7. MEASUREMENTS

- Demographic variables: age, sex, weight, height, comorbidity (ASA grade).
- Variables related to the injury: subcapital fracture, pectrochanteric, subpectrochanteric or others.
- Variables related to the type of surgery: partial hip arthroplasty, endomedullary nailing or others. Duration of surgery.
- Variables related to the response:
 - Latency: evaluated by analgesic scales up to 10 minutes.
 - Analgesic scales: EVN, Algoplus and PAINAD at rest and in activity. They will be carried out upon the patient's arrival at the operating room, continuous until 10 minutes after the nerve block, in the sedation for the subarachnoid block, when they are discharged from the URPA, and at 6, 12, 24 h after the realization of the block, and end of effect after the realization of the block.
 - Need and rescue drugs: rescue analgesia will be scheduled for the hospitalization floor, in case it is necessary. The need, drug and time of administration regarding the realization of the blockade will be collected (Annex II).

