The investigator shall obtain the informed consent of a patient or his/her legal representative before initiating any procedure related to the study, in accordance with the PCBs, as stipulated in the ICH guidelines. It will be recorded in the patient's source documents (medical history) that informed consent has been obtained prior to the patient's entry into the study. The original consent form, signed and dated by the patient and by the investigator will be kept in the study investigator's file. When the investigator proposes to the patient his inclusion in the study, he will inform him in depth about the objectives, possible risks and benefits of his participation, he will answer all the questions that the patient may ask, who will have time to decide his participation in the study. When the patient is legally incapacitated or is not in a position to sign the consent, his legal representative will do so, in accordance with the hospital's policy and the legislation in force in this matter. In the event that a family member signs the consent because the patient is not in a position to sign the consent, and is not legally incapacitated, consent will be requested as soon as possible, when he meets the appropriate conditions, to ratify the consent given by his family.

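### Rescue hangs on the patient's demand and no pain score is tied to it or to the end of analgesia, so any duration read from time to rescue will be missing or overstated in patients who do not ask

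*Combined protocol and SAP*

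**What the plan says.** Annex II (rescue analgesic treatment) instructs staff: "Do not administer scheduled analgesia unless the patient demands it". It also asks for a rescue order to be left in place, says "Evaluate your pain and write down the elapsed time", and moves to a further step if pain persists. Section 6.7 puts rescue more loosely: "rescue analgesia will be scheduled for the hospitalization floor, in case it is necessary". It adds that "The need, drug and time of administration regarding the realization of the blockade will be collected" and points to Annex II.

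On the population, the Introduction says that it "can sometimes have difficulty expressing its feelings, including pain, which is usually underdiagnosed". A secondary objective in section 3.2.2 is to validate, "especially in patients with cognitive impairment, the usefulness of the analgesic scales chosen". Section 7 provides that "When the patient is legally incapacitated or is not in a position to sign the consent, his legal representative will do so", and section 6.8 likewise allows a guardian to be given the consent. Section 6.3, by contrast, requires the patient personally to sign and understand it.

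Section 6.7 and Annex III schedule EVN, Algoplus and PAINAD at discharge from the recovery unit (URPA), at 6, 12 and 24 h after the block, and at the end of its effect. The primary endpoint (sections 1.14 and 6.11) is the duration of the block. No end event is defined.

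**The concern.** The trigger for analgesia in Annex II is something that some patients in scope may not be able to supply. Observer-rated scales are collected with such patients in mind, but no score on any scale releases rescue or marks the end of analgesia.

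Two things are at stake. The first is patient welfare: the instruction, followed to the letter, gives least protection to those least able to speak. The second is the endpoint. Annex III times the period after the block only through the minutes-to-rescue field. The row for the end of the block takes scale scores but has no time, and the latency field concerns onset. If duration is derived from minutes to rescue, a patient who does not ask has either no value or a late one that reflects communication rather than the drug.

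**Working it through.** **Setting the passages side by side**

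- Annex II: demand is the stated trigger. Evaluating pain and noting the time carries no threshold.
- Section 6.7: rescue if necessary, with no criterion for necessity.
- Sections 2, 3.2.2, 6.8 and 7: patients with limited ability to voice pain are in scope.
- Section 6.3: the patient must understand and sign. This conflicts with 6.8 and 7, so the number of such patients cannot be derived.
- Section 6.10: no censoring rule and no time-to-event method, so a patient without rescue has no defined value.

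**The plan's own figure.** Section 6.9 gives 108 patients (54 per arm) for a 3 h difference, a deviation of 50%, alpha 5% and beta 20%, with 10% losses. The base of the 50% is not stated. With n per arm = 2(1.960 + 0.842)² × (SD/3)² = 15.70 × (SD/3)²:

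- SD 6 h (a standardised difference of 0.5): 15.70 × 4 = 62.8, so 63.
- SD 5.25 h (half of an assumed mean of 10.5 h): 15.70 × 3.0625 = 48.1, so 49; 49 × 1.1 = 53.9, so 54.

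The 108 can thus be back-solved but not verified. It serves only as context here.

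**Size of the effect (illustration)**

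From the plan: difference 3 h; 54 per arm less 10% = 48.6, so 49 evaluable. Assumed: means 12 and 15 h; SD 6 h; an equal share q of silent patients in both arms; each recorded at C = 24 h or 48 h; two-sided 5% test.

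- Observed difference = (1 − q) × 3: 2.70 h at q = 10%, 2.55 h at 15%.
- Variance in an arm with mean μ = (1 − q) × 36 + q(1 − q)(C − μ)².
- Example, q = 10%, C = 48 h: 32.4 + 0.09 × 36² = 149.04 and 32.4 + 0.09 × 33² = 130.41. Pooled SD = √139.7 = 11.82; standardised difference 2.70/11.82 = 0.228; t-test power 20%.
- Rise in mean duration in the shorter-acting arm = q(C − 12).

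The t-test column follows from these formulas. Mann-Whitney was simulated (20,000 trials per row, durations clipped to 1-48 h).

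| Silent share, recorded at | t-test power | Mann-Whitney power | Rise in mean, shorter arm |
|---|---|---|---|
| none | 69% | 67% | 0 |
| 10%, 24 h | 53% | 51% | 1.2 h |
| 15%, 24 h | 46% | 44% | 1.8 h |
| 10%, 48 h | 20% | 48% | 3.6 h |
| 15%, 48 h | 15% | 39-40% | 5.4 h |

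The baseline is below 80% only because SD 6 h was assumed. With 10.5 vs 13.5 h and SD 5.25 h, t-test power starts at 80% and falls at q = 10% to 57% (24 h) or 20% (48 h).

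**Is there bias between arms?** With equal true means and 10 to 15% silent patients, the simulated rejection rate stayed between 4.8% and 5.2% for both tests. Four extra silent patients in one arm of 54 would move the difference by 4/54 × 12 = 0.9 h (24 h) or 4/54 × 36 = 2.7 h (48 h), but that is chance imbalance, which alpha covers.

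**The case against.** Three stronger readings are tempting, and the documents do not carry them.

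- *That silent patients go untreated.* The demand wording governs scheduled analgesia. The same annex keeps a rescue order available, has pain evaluated and escalates if it persists, and section 6.7 allows rescue when necessary. Observer-rated scores are taken at fixed times, and staff may act on them. The text is also visibly a translation, so a strict sense of the verb is weak evidence. What stands is that nothing tells staff to act on a score.
- *That these patients are recorded as having a long block.* No section equates block duration with time to rescue or assigns 24 h or 48 h to a patient without rescue, and the end of effect has its own assessment. Section 6.3 may keep some of these patients out. Section 6.6 withdraws those whose scales cannot be evaluated, so some would be lost instead. What stands is that patients who can be scored on PAINAD would remain, and that the form offers no other time from which to derive duration.
- *That the comparison is biased towards one arm.* Randomisation gives equal expected shares and the type I error holds.

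The lowest power figures also need qualifying. Section 6.10 sends non-normal data to Mann-Whitney, and a cluster of values at 48 h would be plainly non-normal, so 15-20% is unlikely to apply. The loss at 24 h is about the same with either test.

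**Conclusion.** The point holds in limited form. Rescue depends on demand in a population for which the protocol itself doubts the ability to express pain, and no collected score is tied to rescue or to the end of analgesia. That inconsistency is in the text and needs no assumption.

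The effect on the endpoint is conditional: it arises if duration is taken from time to rescue. With 10 to 15% silent patients, power would then drop by roughly 15 to 25 percentage points when they are recorded at 24 h, and by about 20 to 27 points at 48 h under Mann-Whitney (about 50 under the t-test). The described mean duration in the shorter-acting arm would be overstated by 1.2 to 5.4 h. The block means, the SD, the silent share and the recorded times are all assumptions; the documents give none of them. The expected harm is dilution and an overstated duration.

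**What to change.** 1. Reconcile Annex II with the Introduction and sections 3.2.2, 6.3, 6.7, 6.8 and 7 on what releases rescue and on who may be enrolled. The clinical rule is for the investigators to set.
2. In sections 1.14 and 6.11, state that analgesia ends at the earlier of (a) the patient's request and (b) the first scheduled pre-rescue assessment at which Algoplus or PAINAD reaches a cut-off that the investigators fix before the first patient.
3. In Annex III, record the time of that event and which of the two triggered it.
4. Treat patients with neither event by the end of follow-up as censored, and add to section 6.10 a method that accepts censoring, such as Kaplan-Meier curves with a log-rank test.
5. Settle the last scheduled assessment: sections 6.7 and Annex III stop the fixed times at 24 h, while section 1.16 refers to a scale at 48 h. This decides how late a score can mark the end.

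The cost is protocol wording, a trigger field with its time, and a changed primary analysis. The scales up to 24 h are already collected. The drawback is that score-triggered times are known only to the nearest scheduled assessment, for example somewhere between 6 and 12 h.

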ANNEX II.- PAIN ASSESSMENT SCALES

[figure not shown]

Figure 1. Numerical Visual Scale

They do not wish to have elements of illustrations.

Figure 2. Algoplus Scale

PAINAD score

Items	0	2	Score
Breathing independent of vocalization	Normal	Occasional labored breathing. Short period of hyperventilation.	Noisy labored breathing. Long period of hyperventilation. Cheyne-Stokes respirations.
Negative vocalization	None	Occasional moan or groan. Low-level speech with a negative or disapproving quality.	Repeated troubled calling out. Loud moaning or groaning. Crying.
Fac to the exprts on	Smiling or inexpressive	Sad. Frightened. Frown.	Facial grimacing.
	Relaxed	Tense. Distressed pacing. Fidgeting.	Rigid. Fists clenched. Knees pulled up. Pulling or pushing away. Striking out.
Consolab Li Ty	No need to console	Distracted or reassured by voice or touch.	Unable to console, distract or reassure.
			Total

Figure 3. PAINAD scale

ANNEX III. DATA COLLECTION NOTEBOOK

Group	Levobupivacaine/Ropivacaine	
Hospital stay	In days	
Age	In years	
Sex	Female/Male	
Weight	In kg	
Size	In m	
Body Mass Index		
Type of Fracture	Subcapital/Petrochanteric/Subpетrochanteric/Other	
Type of Surgery	Partial athroplasty/Interlocking/Other	
Duration of Surgery		
On arrival at the operating room	EVN/Algoplus/Painad	
Latency time		
When sitting	EVN/Algoplus/Painad	
At Discharge of Resuscitation	EVN/Algoplus/Painad	
At 6 o'clock from the blockade	EVN/Algoplus/Painad	
At 12 o'clock of the blockade	EVN/Algoplus/Painad	
Within 24 hours of the blockade	EVN/Algoplus/Painad	
At the end of the blockade	EVN/Algoplus/Painad	
Analgesic rescue	Drug used	
Minutes to rescue	Time elapsed from lock to rescue	
Morphic equivalence	Equivalence in morphics of the rescue used	
Nausea and vomiting		
Toxicity	Toxicity developed by local anesthetics	
Delirium		
Infection	Clinically and analytically diagnosed	
Exitus		

BIBLIOGRAPHY

2. Tim JS Chesser DI, Antony Johansen, Alberto Belluati, Carlota Pari, Achile Contini, Stijn C Voeten, Johannes H Hageman, Kornelis J Ponsen, Nuria Montero-Fernández, Alberto Delgado-Martínez, Francisco Chana-Rodríguez Hip fractur systems-European experience. *OTA International.* 2020;3(1):1-6.
4. Fernández [name] M MJ, Olmos JM, [name]-[name] J, Hernández JL. Review of the incidence of hip fracture in Spain. *Rev Osteoporos Metab Miner.* 2015;7(4):115-20.

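### The only rescue quantity in Annex III, morphine equivalence, is zero for every non-opioid rescue, so it measures opioid exposure and reflects analgesic need only coarsely

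*Combined protocol and SAP*

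**What the plan says.** Section 6.7 places rescue among the response variables: "The need, drug and time of administration regarding the realization of the blockade will be collected". Section 6.8 adds that treatments the patient needed are recorded throughout. Annex III turns this into three rows: drug used, minutes from block to rescue, and morphine equivalence, described as "Equivalence in morphics of the rescue used". It gives no conversion factor, time window or rule for non-opioid drugs. It has no row for rescue dose, number of administrations or NSAID contraindication.

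The rescue scheme in Annex II (rescue analgesic treatment) has three steps:

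- Step 1 is paracetamol, "1 gr/ 6 h iv. If contraindication or allergy: Metamizol 2g/8 h iv".
- Step 2, dexketoprofen every 8 h, applies "If you need more analgesia and the 6 h has not passed".
- Step 3 applies "If contraindication to NSAIDs or pain persists". It is a tramadol "infusion 200 mg iv" combined with metamizole "6 gr diluted in 500 cc S. Physiological to pass in 24 h (20ml/h".

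The annex closes with "Follow-up of the patient 48 h".

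Morphine equivalence is not among the main or secondary variables in section 1.14. Section 6.10 gives it no analysis of its own, but plans between-arm tests for the variables collected in general terms.

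**The concern.** A quantity for rescue would ordinarily be read as how much extra analgesia each arm needed. Section 2.1 presents less concomitant analgesia as a benefit of the block, and the hypothesis in section 3.1 includes better analgesic control with levobupivacaine. A score built only from opioid content cannot register differences in paracetamol, metamizole or dexketoprofen use.

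Step 3 also has two separate triggers, so a non-zero score can mean either that pain persisted or that the patient could not take an NSAID. The introduction says NSAIDs may affect already decreased renal function in these patients, so the second route is foreseeable. The regression planned in section 6.10 cannot adjust for contraindication if it is not recorded.

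What is at stake is the usefulness of the rescue comparison, not the main result.

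**Working it through.** The plan states no figure to reproduce here. The check traces Annex II against the Annex III field.

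**Score by pathway.** Let k be the tramadol-to-morphine conversion factor, which the documents do not give.

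- No rescue: 0.
- Step 1 only: 0. The stated interval allows 48/6 = 8 paracetamol doses in the 48 h follow-up.
- Steps 1 and 2: 0. The stated interval allows 48/8 = 6 dexketoprofen doses.
- Step 3, one infusion: 200k. A second infusion within 48 h would give 400k, and one stopped early would give less.

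The stated rate of 20 ml/h against 500/24 = 20.8 ml/h is rounding (200/500 × 20 × 24 = 192 mg in 24 h) and does not affect the point.

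**Two patients with the same need beyond step 1.** The one who can take an NSAID receives dexketoprofen and scores 0 if it works. The one who cannot goes from step 1 to step 3 and scores 200k.

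**Sensitivity to a real difference.** Let q be the share needing more than step 1, c the share with an NSAID contraindication, and r the share whose pain persists after dexketoprofen. None is in the documents. I assume c = 10–50% and r = 30–50%, equal in both arms.

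- Share with a non-zero score = q × [c + (1 − c) × r].
- Lowest multiplier: 0.10 + 0.90 × 0.30 = 0.37. Highest: 0.50 + 0.50 × 0.50 = 0.75.
- A 10-point difference between arms in q therefore becomes 3.7 to 7.5 points on the score.
- A difference only in how many patients need step 1, or in how many step 1 or step 2 doses they need, becomes 0.

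**Share of non-zero scores due to contraindication alone** (patients dexketoprofen would have controlled) = c(1 − r) / [c + (1 − c)r]; q cancels.

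- c = 10%, r = 50%: 0.05/0.55 = 9%.
- c = 50%, r = 30%: 0.35/0.65 = 54%.

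**Chance imbalance in contraindication, 54 per arm.** The standard deviation of the difference in proportions is √[2c(1 − c)/54].

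- c = 20%: 0.077, so a gap of 10 points or more has probability about 19%.
- c = 50%: 0.096, probability about 30% (normal approximation).
- Such a gap moves the share scoring above zero by only 10 × q × (1 − r) points. With assumed q = 30–60% and r = 30–50%, that is 10 × 0.30 × 0.50 = 1.5 to 10 × 0.60 × 0.70 = 4.2 points, or 54 × 0.015 = 0.8 to 54 × 0.042 = 2.3 patients per arm.

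**The case against.** The strongest reply is that the field is not an endpoint. It appears only in Annex III, and no section says it will stand for rescue consumption. Need, drug and time are also collected. Read as opioid exposure it is correct: the introduction names avoiding opioids as a goal, zero is the right value for a patient managed without them, and a patient given tramadol was exposed whatever the reason. All of this stands, and it is why the field should be relabelled rather than condemned. It does not supply a measure of how much rescue was needed, because need, drug and time to rescue contain neither dose nor count.

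A second reply is that Annex III may be a list of variables rather than the full form: the adverse-event sheet mentioned in section 6.13 is not shown there either. Doses may also be recoverable from the medical record, which section 6.14 makes the data source. That is fair. The gap is in what the plan specifies, and the data may still exist.

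A reader might infer that a chance excess of NSAID contraindication in one arm would pass for a drug effect, and take the 19–30% above as the risk. The documents do not support that. Allocation is randomised (section 6.5), so with no drug effect a valid test keeps its 5% error rate whatever baseline factors drive the outcome. The imbalance is already part of the sampling variation. The 19–30% is the chance of a baseline gap, not of a false finding.

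A reader might also infer that the score is unrelated to need. It is not: persisting pain is one of the two triggers for step 3, and contraindication skips only step 2, since step 1 still comes first.

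**Conclusion.** The point holds as a limitation of measurement. The one rescue quantity in Annex III is structurally zero for all non-opioid rescue and close to a yes/no marker for the tramadol infusion. It measures opioid exposure. As a measure of analgesic need it is coarse, insensitive and partly dependent on NSAID eligibility, which is not recorded. Under the assumed rates it passes on roughly 37% to 75% of a true difference in need beyond step 1, and none of a difference within steps 1 and 2. Between 9% and 54% of non-zero scores would come from contraindication alone. These figures rest on assumed values of c and r; the zero for non-opioid rescue follows from Annex II itself.

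The primary endpoint, block duration, and the secondary variables listed in section 1.14 are unaffected. This is a cheap improvement worth making, not a threat to the trial's main conclusion.

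**What to change.** - **Annex III:** replace the single rescue entry with one line per administration (drug, dose, time from block) through the existing 48 h follow-up. Add NSAID contraindication at baseline.
- **Sections 6.7 and 6.10:** name the number of rescue administrations and the highest Annex II step reached as the between-arm rescue measures, alongside time to first rescue.
- **Morphine equivalence:** keep it, or reduce it to tramadol yes/no, labelled as opioid exposure rather than rescue consumption and described by NSAID contraindication. If the numeric form is kept, state the conversion factor and the time window.

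The cost is one edited form page, a sentence in each of the two sections, and slightly more data entry. No change to rescue treatment is proposed.
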